Quantitative data: We will use descriptive statistics (i.e., frequencies, means and standard deviation estimates) to describe the analytical sample. We will examine whether the implementation strategies (i.e., advisory board, use of REDCap handheld tablets, use of the PSC tool and an implementation coach) increases the number of children screened and referred to support services, compared to baseline. To do that, we will use methodology that accounts for repeated measures over time and that accounts for both within-person and across-person variation (i.e., Generalized linear mixed model (GLMM)) while controlling for clustering of patients within clinics and possible confounding by calendar time. *Our analysis will include sex as a biological variable, testing for a differential effect on outcomes by child sex.* We will report the magnitude of missing data and compare demographic and clinic characteristics and outcomes between observations with versus without missing data. In sensitivity analyses, we will perform multiple calculations (i.e., imputations) using fully conditional specification to obtain 10 complete datasets; summary estimates of intervention effects with 95% confidence limits over the 10 datasets will incorporate within- and between-dataset sampling variability.

Comparison of randomized intervention sites to non-randomized control sites

Due to the human and financial impact of COVID-19 epidemic, the randomized control periods had not implemented ACEs screening at the time of the pilot starting. We have identified two clinics that have implemented ACEs screening that are not part of the trial.

To obtain an additional non-randomized estimate of the intervention effect, we will compare:

- (1) the control periods in the randomized clinics to comparable time periods in the non-randomized clinics;
- (2) the intervention periods in the randomized clinics to comparable time periods in the non-randomized clinics.

We will use the same GLMM models as described above, with indicator variables for non-randomized vs randomized clinic, and randomized control vs intervention periods. Groups will be compared on ACEs screenings, and mental health referral rates.

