ACCORDS

ADULT AND CHILD CENTER FOR OUTCOMES
RESEARCH AND DELIVERY SCIENCE

UNIVERSITY OF COLORADO
CHILDREN'S HOSPITAL COLORADO

Supporting the Implementation of a State Policy on Screening for Adverse Childhood
Experiences (ACEs) in Federally Qualified Health Centers (FQHC).

Statistical Analysis Plan

NCT: 04916587

Date: 7.20.2024

Statistical Analysis Plan

Title of Study: Supporting the Implementation of a State Policy on Screening for Adverse Childhood Experiences (ACEs) in Federally Qualified Health Centers (FQHC)

NIMH Study ID Number: R21MH123835

Clinical Trial Number: NCT04916587

Sponsor: Study funded by the National Institute of Mental Health.

Principal Investigator: [name] [name].

Summary and research objective(s):

Screenings for Adverse Childhood Experiences (ACEs) promote early identification of toxic stress and potential trauma, allowing for intervention and possible amelioration of detrimental effects of the ACEs. The state of California enacted a 2020 fee-for-service healthcare policy, ACEs Aware, reimbursing clinics for annual ACEs screenings during well-child visits, but did not provide guidance on screening implementation. This study aims to test the effectiveness and acceptability of a multifaceted implementation strategy for implementing ACEs screenings, in partnership with a Federally Qualified Health Center (FQHC) system in California that adopted the ACEs Aware policy in August of 2020.

The proposed strategy is comprised of personnel training (e.g., Trauma-informed care), integrated technology with a customized screening scoring and aligned service referral algorithm, team-based screening workflows, ongoing care team coaching, and peer support. Significant changes to the original study protocol were needed to accommodate the negative impact that the COVID-19 pandemic had in the partner FQHC system.

Hypotheses

1. ACEs screenings

- a. Clinics using implementation strategies will have higher rates of REACH of ACEs screenings compared to their screening rates before implementing the strategies.
- b. Clinics using implementation strategies will have higher rates of REACH of ACEs screenings than clinics screening for ACEs and as part of the state funded CALQIC project, without the implementation strategies.

- c. Exploratory: Are there any differences between in the effectiveness of the implementation strategies in different sub-groups (such as race, ethnicity, age and gender)?

2. Referrals to mental health services

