- a. Clinics using implementation strategies will have higher rates of mental health referrals compared to their referral rates before implementing the strategies.
- b. Clinics using implementation strategies will have higher rates of mental health referrals than clinics screening for ACEs and as part of the state funded CALQIC project, without the implementation strategies.
- c. Among children screened, ACEs screenings indicating medium and high risk will lead to mental health referrals at higher rates than screenings indicating low risk.
- d. Exploratory: Are there any differences between in the effect of the implementation strategies on referrals in different sub-groups (such as race, ethnicity, age and gender)?

[figure not shown]
3. Implementation outcomes

- a. Perceive feasibility, acceptability, and usefulness of the intervention will be sufficiently high (see Table 1).

Study design:

Changes to the original study design were needed to accommodate the negative impact that the COVID-19 pandemic had in the partner FQHC system. We conducted a stepped-wedge design (SWD) trial with three sites, with data collection divided into 7 10-week intervals. Study sites remained in the intervention phase for multiple intervals to allow additional data to be collected. In addition to the 3 study sites, 2 additional sites from the same health system served as comparison sites, implementing ACEs screenings without the support of the implementation strategies. See Figure 1 for the SWD schedule.

Figure 1. Stepped-wedge schedule for the ACEs pilot study.

Study sites and patient eligibility:

The study statistician originally selected five clinics from a pool of 16 clinics providing family medicine, pediatric, or primary care for children ages 0 to 5 years old and across five regions to maximize variation (e.g., clinic characteristics such as resources and size). Clinics were located in urban, suburban, rural, and frontier communities. The study PI and FQHC champions invited the identified clinics via email to an informational video session to introduce the study and provided study informational materials to the clinic manager.

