Descriptive statistics will be used to describe the sample of children and clinics. The sample will be described using counts and percentages, and treatment groups will be compared using chi-squared tests. We will calculate risk differences with confidence limits for each of our three groups of interest- the study clinics during the control period, study clinics during the intervention period, and the control clinics. For subgroup analyses exploring differences by child demographics, we will calculate risk differences within those subgroups (age, gender, race, and ethnicity).

The reach variable (proportions screened) will be analyzed using binary regression (a generalized linear model, specifying a binomially-distributed dependent variable and identity link function). Modified Poisson regression with robust variance estimation¹⁴ will be used to analyze mental health referrals to estimate adjusted risk differences. Both models will compare the intervention and control arms as the primary independent variable of interest. Possible covariates will include child's sex, age category (<18 months, 18-60 months), child's race (white, black, other/unknown), child's ethnicity (Latino, not Latino, unknown/not reported), language of preference, and study site; covariates will be included in their adjustment changes the intervention regression coefficient by more than 15%.

Models comparing the intervention and comparison clinics will be adjusted for the child's race and for the study site. Missingness in demographic data will be handled by including an 'unknown or not reported' category. Survey data will be analyzed using aggregated intra-class correlations (ICC) to assess within-group agreement, whether clinic care teams shared perceptions of readiness for change during the preparation phase, and implementation climate and leadership. ICC is the variance proportion attributed to care teams.¹⁵ Higher scores in these measures reflect higher organizational support for the translation of a new clinical practice into practice.¹⁶ An agreement of 0.70 or higher reflects an organizational measure.¹⁷

References

1. National Pediatric Practice Community. PEARLS FAQs. Accessed August 14, 2019. <https://nppcaces.org/faqs/>
2. Aware A. ACES Screening Clinical Workflows. Accessed June 15, 2020. <https://www.acesaware.org/wp-content/uploads/2019/12/ACE-Clinical-Workflows-Algorithms-and-ACE-Associated-Health-Conditions.pdf>

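### The SAP asks whether the effect differs between subgroups but plans only risk differences within each one, and the protocol's test by child sex is not carried over

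*SAP*

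**What the plan says.** Under Hypotheses, the SAP poses an exploratory question for each main outcome. For reach (1c): "Are there any differences between in the effectiveness of the implementation strategies in different sub-groups (such as race, ethnicity, age and gender"). For referrals (2d), it asks about differences "in the effect of the implementation strategies on referrals in different sub-groups (such as race, ethnicity, age and gender").

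Under Statistical analysis, the answer offered is that "we will calculate risk differences within those subgroups (age, gender, race, and ethnicity"). The sentence before it reads "We will calculate risk differences with confidence limits for each of our three groups of interest"; confidence limits are not mentioned again for the subgroups. On the regressions, the SAP says "Both models will compare the intervention and control arms as the primary independent variable of interest". Sex, age, race and ethnicity enter these models only as candidates for adjustment ("Possible covariates will include child's sex, age category (<18 months, 18-60 months"), kept if they move the intervention coefficient by more than 15%. Race is also a fixed adjustment in the models against the comparison clinics.

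The protocol (section V, Data Analysis) goes further for one factor. It treats sex as a biological variable and commits to "testing for a differential effect on outcomes by child sex".

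**The concern.** A question about whether an effect differs is a question about a contrast between subgroups. The SAP stops at the components of that contrast. It names no interaction term, no difference of risk differences and no heterogeneity test. Adjusting for sex does not fill the gap: a main effect for sex changes the overall estimate but says nothing about whether the effect varies by sex.

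Two things are at stake. First, with only separate estimates in the report, a difference may be inferred because one interval excludes zero and another does not, which is not evidence that the effects differ. The scope for this is wide. Taking sex as two levels and the SAP's categories for age (2), race (3) and ethnicity (3) gives 10 subgroup levels. Over two outcomes and two comparisons (before v after, and v comparison clinics) that is up to 10 × 2 × 2 = 40 risk differences. A false claim of an ethnic or sex difference would matter in a study whose own rationale raises the risk of widening disparities.

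Second, a commitment in the protocol is missing from the SAP. Both documents carry the same cover date. The SAP attributes its design changes to the pandemic's effect on the clinic system, which does not explain dropping an analysis by sex.

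**Working it through.** **Text check.**

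| Place | What it commits to |
|---|---|
| SAP Hypotheses 1c, 2d | Whether the effect differs between subgroups |
| SAP Statistical analysis, subgroups | A risk difference within each subgroup |
| SAP Statistical analysis, models | Arm as main effect; sex, age, race and ethnicity as possible covariates |
| Protocol V, Data Analysis | A test of differential effect by child sex |

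The second and third rows, followed exactly, produce neither the first nor the fourth.

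**Size of the misreading risk.** The readable text gives no sample size per arm, subgroup size, alpha or power for these analyses, so there is no planned figure to reproduce. What follows is an illustration.

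Inputs from SAP Table 1: current referral rate 3.8%, and an expected increase of 11.4%. The wording leaves open a rise *to* 11.4% or *by* 11.4 points (3.8 + 11.4 = 15.2%), so both are shown. Assumed: two-sided 0.05, two equal and independent subgroups, the same true effect in both, no clustering by clinic.

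Let p be the power within one subgroup. This is the exact binomial probability that an unpooled two-proportion z test has |z| > 1.96. The chance that exactly one of two subgroups is significant is 2p(1 − p). At 100 per arm per subgroup, 3.8% v 11.4%: p = 0.558, and 2 × 0.558 × 0.442 = 0.493.

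| Children per arm per subgroup | p, 3.8% v 11.4% | Exactly one significant | p, 3.8% v 15.2% | Exactly one significant |
|---|---|---|---|---|
| 50 | 0.335 | 45% | 0.550 | about 50% |
| 100 | 0.558 | 49% | 0.826 | 29% |
| 150 | 0.727 | 40% | 0.944 | 11% |
| 200 | 0.842 | 27% | 0.984 | 3% |
| 300 | 0.953 | 9% | 0.999 | under 1% |
| 400 | 0.987 | 2.5% | over 0.999 | under 1% |

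A pooled z test gives 41%, 50%, 41% and 28% at 50 to 200 for the 11.4% reading, so the choice of test matters little. A valid test of the between-subgroup contrast would declare a difference in a nominal 5% of such trials.

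**Reach.** Table 1 expects 80% to 92% screened, and the protocol says the control periods had not implemented screening. With 0% or 10% v 80%, p is effectively 1 at 50 or more per arm per subgroup, so the chance that exactly one is significant is close to zero.

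**What the missing contrast would deliver.** For independent subgroups it is RD1 − RD2, with SE = √(SE1² + SE2²). At 100 per arm per subgroup, 3.8% v 11.4% in both:

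- SE of each RD = √[(0.038 × 0.962 + 0.114 × 0.886)/100] = 0.0371
- SE of the difference = √2 × 0.0371 = 0.0525
- 95% half-width = 1.96 × 0.0525 = 0.103, or 10.3 points, against a subgroup effect of 7.6 points

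At 400 per arm per subgroup the half-width is 5.1 points.

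Power of the contrast by normal approximation, with 100, 225, 450 and 900 children per arm split equally into two subgroups:

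| True pattern | Rise to 11.4% | Rise to 15.2% |
|---|---|---|
| Full effect in one, none in the other | 22%, 42%, 70%, 94% | 38%, 70%, 94%, over 99% |
| Full effect in one, half in the other | 8%, 13%, 21%, 37% | 11%, 20%, 36%, 62% |

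**The case against.** A reader might infer that the subgroup question cannot be answered at all. The documents do not support that. Within-subgroup risk differences are the right components on the right scale, and the formula above turns them into the contrast if each comes with a valid standard error or interval. What is missing is a pre-specified contrast, not the data.

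It can also be said that the SAP plans estimates, not subgroup significance tests, and nowhere says it will set a significant subgroup against a non-significant one. That is correct: the misreading is a risk in reporting, not a stated plan. It is a foreseeable risk, because nothing else planned speaks to the question.

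A reader might extend the 27% to 49% range to the whole trial. It does not extend. It applies to referrals at 50 to 200 children per arm per subgroup under the 11.4% reading. It falls away at larger sizes, is mostly lower under the 15.2% reading, and vanishes for reach. The main outcomes come from the electronic medical record, so small subgroups cannot be presumed. An even split is plausible for sex but undocumented for race and ethnicity.

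Nor is sex ignored: gender remains a named subgroup and sex a candidate covariate. Only the formal test is gone.

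Finally, 1c and 2d are labelled exploratory, this is a pilot, and the contrasts will be imprecise. This lowers the priority. It does not remove the mismatch, since an exploratory question still needs an estimate that addresses it, and the protocol does not label its sex test exploratory.

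**Conclusion.** The point holds as a mismatch between question and method. The SAP specifies no between-subgroup contrast, so no planned analysis formally answers 1c or 2d, and the protocol's test by child sex is dropped without a stated reason. No main comparison is affected. It should be corrected, but it does not threaten the trial's main conclusions.

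The textual finding needs no assumptions. The size does: for referrals, with identical effects in two subgroups, exactly one is significant in anything from about half of trials to about 2.5% over 50 to 400 children per arm per subgroup (3.8% v 11.4%), and in under 1% from 300 upwards if the rise is to 15.2%. These figures rest on assumed subgroup sizes, equal and independent subgroups, and no clustering. With three study clinics, real precision may be lower.

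**What to change.** - In both outcome models, add intervention-by-subgroup terms on the risk-difference scale: one each for sex and age category, two each for the three-level race and ethnicity variables (1 + 1 + 2 + 2 = 6 per outcome and comparison, entered one factor at a time).
- Report each difference between subgroup risk differences with a 95% confidence interval, handling clinic and calendar time as in the main model.
- State which comparison (before v after, v comparison clinics, or both) the subgroup questions concern.
- State confidence limits for the within-subgroup risk differences and keep them as description.
- Restore the protocol's test of differential effect by sex, or record why it was dropped.
- Label all these results exploratory and low-powered.

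No new data are needed. The cost is a few model terms and sentences, wide intervals, and several exploratory contrasts without multiplicity control, which the report should acknowledge. Where control reach is near zero, the identity-link model may be hard to fit with added terms. The contrast can then be formed from the subgroup risk differences and their standard errors, provided those standard errors allow for clinic.

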Once the pilot study started, two randomly selected clinics were not able to participate - one clinic closed and one clinic lost their pediatrician leading ACEs screenings. Due to extremely high staff turnover at the clinics and among FQHC leadership, additional clinics selected were not able to participate in this research study. Thus, from the three clinics that finished the stepped wedge schedule, one was randomly selected and two clinics joined based on their capacity to participate in a research study at that time.

Eligible children were those aged 0-5, on public insurance, attending a wellness visit with the participating clinician.

Data sources:

Data for the primary outcomes, including reach of ACEs screenings and mental health referral rates, was obtained via the electronic medical record (EMR) at the partner health system. Additional data for secondary analyses was collected using REDCap among intervention patients only, including the PSC scores and ACEs screening results. See Figures 2 and 3 for the Consort tables.

Figure 2. CONSORT table for the study pilot study – Electronic Medical Records Data.

[figure not shown]

Figure 3. CONSORT table for sub-sample of data – REDCap system.

[figure not shown]

Table 1. Description of measures

Measure	Description/psychometrics	Source
ACEs Screening		
PEARLS¹ screening (ages 0-11)	Caregiver-reported tool (17-items) designed to identify exposure to childhood adversity and stress factors that may lead to toxic stress and negative health outcomes. Number of endorsed events are summed up (0-4+) to identify risk level for toxic stress and potential symptomatology. English/Spanish	Caregiver
ACEs associated health conditions²	State-sponsored list with 25 ACEs associated health conditions for children ages 0 – 5. ² Physical conditions include asthma, allergies, unexplained somatic symptoms such as headaches. Mental health related conditions (over 10) include aggression, depression, ADHD, and anxiety	EMR system

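### The H2a referral model names no variance unit and has no interval or clinic-by-interval term, although the strategy is switched on by clinic and 10-week interval

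*SAP*

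**What the plan says.** Hypothesis 2a in the SAP is a before/after comparison inside the study clinics: "Clinics using implementation strategies will have higher rates of mental health referrals compared to their referral rates before implementing the strategies". Under Study design the SAP states: "We conducted a stepped-wedge design (SWD) trial with three sites, with data collection divided into 7 10-week intervals". The crossover schedule is in a figure that is not shown. Under Data sources, referrals are one of the primary outcomes.

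Under Statistical analysis, modified Poisson regression with robust variance "will be used to analyze mental health referrals to estimate adjusted risk differences". The main term is intervention against control: "Both models will compare the intervention and control arms as the primary independent variable of interest". The candidate covariates are child characteristics, ending with "language of preference, and study site". They enter by a change-in-estimate rule: "covariates will be included in their adjustment changes the intervention regression coefficient by more than 15" per cent. Adjustment for race and study site is fixed in advance only for models that bring in the comparison clinics, so in H2a study site may drop out. Calendar time and interval are not on the list. No cluster unit is given for the robust variance.

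The protocol (section V, Data Analysis) plans a generalized linear mixed model for screening and referral, "while controlling for clustering of patients within clinics and possible confounding by calendar time". It names no clinic-by-interval effect either. Neither document states a significance level for H2a. The number of eligible children per clinic and interval does not appear in the available text.

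**The concern.** The strategy changes status for a whole clinic at an interval boundary. The replication for the H2a contrast is therefore the clinic-interval, not the child. A robust variance computed over individual children corrects the Poisson variance for a binary outcome, but it treats children in the same clinic and interval as independent. If a clinic's referral rate moves between intervals for reasons unrelated to the strategy, the model has no term for that movement, and it passes into the intervention coefficient with a standard error that ignores it.

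This component differs from two others that are often discussed. Level differences between clinics cancel in a before/after contrast, provided that study site is in the model. A calendar trend shared by all clinics can be removed by interval terms. A swing specific to one clinic in one interval is removed by neither. At stake are the confidence limits for a primary outcome: chance movement between intervals could be reported as an effect of the strategy, in either direction.

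**Working it through.** The documents give no power, sample size or type I error figure for H2a, so there is no stated figure to reproduce.

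**Inputs from the documents.** Three clinics and seven intervals (SAP, Study design): 3 × 7 = 21 cells. Current referral rate 3.8% (SAP, Table 1).

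**Assumptions.** m = 50, 100 or 200 eligible children per cell, equal across cells. Clinic-interval ICC from 0 to 0.02. Crossover after intervals 1, 2 and 3. Two-sided 5% level. Study site in the model. No strategy effect and no common trend.

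**What the ICC means.** The SD of the true interval rate is √(ICC × 0.038 × 0.962). At ICC 0.001, 0.005, 0.01 and 0.02 this is 0.6, 1.4, 1.9 and 2.7 percentage points around 3.8%. As a fraction of 3.8% (the CV) it is 16%, 36%, 50% and 71%.

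**Reading 1: child-level robust variance.** The variance is understated by DEFF = 1 + (m − 1) × ICC, and type I error = 2 × [1 − Φ(1.96/√DEFF)]. Example: m = 100, ICC 0.01 gives DEFF = 1.99, 1.96/√1.99 = 1.389, type I error 16.5%.

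Each entry is the closed form, with the simulated value (4,000 runs, linear risk model) in brackets where that set-up was run:

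| ICC | m = 50 | m = 100 | m = 200 |
|---|---|---|---|
| 0 | 5.0 (5.7) | 5.0 (5.4) | 5.0 (4.9) |
| 0.001 | 5.6 | 6.2 | 7.3 |
| 0.005 | 7.9 (8.6) | 10.9 (10.6) | 16.5 (17.1) |
| 0.01 | 10.8 (11.8) | 16.5 (16.2) | 25.7 (26.3) |
| 0.02 | 16.4 (17.1) | 25.6 (26.0) | 38.0 (37.9) |

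The multiple of nominal runs from 1.0 to 38.0/5 = 7.6. A separate simulation of the log-link modified Poisson model (3,000 runs per setting) agrees with the closed form or runs slightly lower. At m = 300 and CV 0.2, 0.3 and 0.5 it gives 10.1%, 18.0% and 31.8%, against 10.6%, 17.2% and 32.4%.

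**Reading 2: robust variance clustered on the three clinics, normal reference.** Simulated type I error is 24–28%, whatever the size of the swing, because three clusters are too few for the sandwich estimator.

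**Does adding calendar time suffice?** No. With interval terms in the child-level model, clinic-specific swings still give 9.0% (m = 100, CV 0.3) and 31.5% (m = 300, CV 0.5). Interval terms are still needed: with swings shared by all clinics and no time term, the child-level test gives 9.1–24.2% at m = 100 and 16.3–43.8% at m = 300 (CV 0.2–0.5).

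**Does a clinic-interval analysis hold the level?** Regressing the 21 proportions on intervention status with clinic effects leaves 21 − 1 − 2 − 1 = 17 df. Under independent clinic-specific swings it gives 4.2–5.8% for every cell size, CV and schedule tried. Without interval terms it gives 6.2–16.4% under shared swings, so they belong in the model, leaving 17 − 6 = 11 df. With independent swings the analysis holds 4.2–5.9% with or without them. If swings persist across intervals (AR(1), correlation 0.5), the version without interval terms gives about 5–9%.

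**The case against.** A reader might infer from the upper cells of the table that the planned test runs at several times its nominal level. The documents do not support that as a statement about this plan. Cell size, ICC and schedule are all assumed, and an ICC of 0.02 means a swing of 71% of the mean rate. At ICC 0.001 the error stays below 8%. The only size clue is the 450 children whose results are kept in REDCap (protocol, Data storage plans). Spread over an assumed 12 to 15 intervention cells at the 80–92% reach in Table 1, that gives 450/(15 × 0.92) ≈ 33 to 450/(12 × 0.80) ≈ 47 per cell. Type I error is then 5.6–10.4% for CV 0.2–0.5, or 1.1 to 2.1 times nominal. This stands as a caution. But the 450 are a research sub-sample, whereas the H2a denominator is all eligible children in the medical record, so real cells may be larger.

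A reader might also take the staffing sentence that begins "Due to extremely high staff turnover at the clinics and among FQHC leadership" as evidence of such swings. It explains why further selected clinics could not take part. It does not report movement in referral rates at the three clinics that finished. Swings are plausible, not documented.

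Nor does the SAP say that the robust variance is at child level; that is the usual application, but an inference here. Clustering on clinic removes this mechanism and brings in the three-cluster problem, so the objection does not rescue the analysis.

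Finally, H2a is directional and the figures are two-sided. In the linear-risk simulations 55–65% of false rejections favoured the strategy (6.8 of 11.4 points at m = 50, ICC 0.01). In the log-link simulations it was about half (15.7 of 31.8 at m = 300, CV 0.5). Not every false rejection would be a false claim of benefit, but the width of the limits does not depend on direction.

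**Conclusion.** The point holds as a gap in specification with a conditional consequence. What the documents show without any assumption is that the H2a model names no variance unit, has no interval or clinic-by-interval term, lets study site drop out, and departs from the protocol on clustering and calendar time. What follows depends on the reading. With child-level variance the test is sound if rates do not swing. Otherwise type I error is about 5.5–8% at ICC 0.001, 8–17% at 0.005, 10–26% at 0.01 and 17–38% at 0.02, for 50 to 200 children per cell. With variance clustered on three clinics it is about 24–28%. These figures rest on the 3.8% rate in the SAP and on assumed cell sizes, ICC, crossover schedule and a two-sided 5% level. No figure was computed for reach (H1a), but its model has the same main term and the same missing terms. A return to the protocol's mixed model as described would settle the conflict between the documents and deal with a shared trend, but not with clinic-specific swings.

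**What to change.** For H2a, and for the H1a limits, take the error term from clinic-interval variation. Regress the 21 clinic-interval proportions on intervention status with clinic fixed effects and interval terms, using a t reference on 11 df. Alternatively, fit a model with clinic, calendar-time and clinic-by-interval effects and a small-sample df correction. Report those limits as primary. Keep the child-level model for covariate-adjusted point estimates, retain study site in it whatever the 15% rule gives, and state its variance unit. State the significance level and sidedness. Reconcile the SAP's Statistical analysis with the protocol's Data Analysis section, so that one model is named for referrals.

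The cost is SAP wording and a re-run on data already collected by interval. The limits will be wider and rest on few degrees of freedom. Swings that persist across intervals would still leave modest inflation (about 5–9% in the version without interval terms), which should be reported as a limitation.
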